8.2. Subject Disposition and Population Assignment

Subject disposition and population assignment will be listed. A summary table by treatment will be provided, based on the safety population.

8.3. Screening Demographics

The screening demographics including age, sex, height, body weight, and body mass index will be listed. A separate summary table by treatment will be provided, based on the safety and PK populations.

8.4. Prior and Concomitant Medication

Prior medication will be defined as medication that ends prior to the first dose. Concomitant medication will be defined as medication that starts during or after the first dose or starts but does not end prior to the first dose.

Prior and concomitant medications will be coded using the World Health Organization Drug Dictionary (WHODrug) Global, Format B3, Version September 2020 (or later if a new version is issued during the study; see the data management plan [DMP] for more details). Prior and concomitant medications will be listed.

8.5. Pharmacokinetic Assessments

8.5.1. Pharmacokinetic Analysis

The following PK parameters will be determined where possible from the plasma and urine concentrations of AM1476 using noncompartmental methods in validated software program Phoenix WinNonlin (Certara, Version 8.1 or higher):

Parameter	Units ^a	Definition
AUC _{0-tlast}	ng*h/mL	area under the concentration-time curve from time 0 to the time of the last quantifiable concentration $(t_{last})^b$
$AUC_{0-\infty}$	ng*h/mL	area under the concentration-time curve from time 0 extrapolated to infinity ^{b,c}
C _{max}	ng/mL	maximum observed concentration
t _{max}	h	time of the maximum observed concentration
t _{last}	h	time of the last quantifiable concentration
t _{1/2}	h	apparent terminal elimination half-life
CL/F	L/h	apparent total clearance
V_Z/F	L	apparent volume of distribution during the terminal phase
CL _R	L/h	renal clearance
Ae _{t1-t2}	mg	amount of the dose administered recovered over the time interval t1 to t2
fe _{t1-t2}	0⁄0	percentage of the dose administered recovered over the time interval t1 to t2
DAUC _{0-tlast}	h*ng/mL/mg	AUC _{0-tlast} normalised by dose administered ^d
$DAUC_{0-\infty}$	h*ng/mL/mg	$\mathrm{AUC}_{0\text{-}\infty}$ normalised by dose administered ^d
DC _{max}	ng/mL/mg	C _{max} normalised by dose administered ^d

Part A (Single Dose)

Abbreviations: AUC = area under the concentration-time curve; PK = pharmacokinetic(s).

a. Units are based on concentration units (provided by the bioanalytical lab or preferred units for presentation of PK parameters) and dose units used in the study.

b. The AUC will be calculated using the linear trapezoidal rule for increasing concentrations and the logarithmic rule for decreasing concentrations (linear up/log down rule).

c. Based on the last observed quantifiable concentration

d. Calculated by dividing the parameter by the dose (mg)

Parameter Units ^a Definition		Definition	
AUC _{0-τ}	ng*h/mL	area under the concentration-time curve over a dosing interval $(\tau)^{b}$	
$AUC_{0-\infty}$	ng*h/mL	area under the concentration-time curve from time 0 to infinity (Day 1 only) ^{b,c}	
C _{max}	ng/mL	maximum observed concentration	
C_{min}	ng/mL	minimum observed concentration	
t _{max}	h	time of the maximum observed concentration	
t _{1/2}	h	apparent terminal elimination half-life	
CL/F	L/h	apparent total clearance	
V_Z/F	L	apparent volume of distribution during the terminal phase	
RA _{AUC0-τ}		observed accumulation ratio based on $AUC_{0-\tau}$	
RA _{Cmax}		observed accumulation ratio based on C _{max}	
CL _R	L/h	renal clearance	
Ae _{t1-t2}	mg	amount of the dose administered recovered over the time interval t1 to t2	
fe _{t1-t2}	%	percentage of the dose administered recovered over the time interval t1 to t2	
DAUC _{0-τ}	h*ng/mL/mg	$AUC_{0-\tau}$ normalised by dose administered ^d	
DC _{max}	ng/mL/mg	C _{max} normalised by dose administered ^d	

Part B (Multiple-dose)

Abbreviations: AUC = area under the concentration-time curve; PK = pharmacokinetic(s).

a. Units are based on concentration units (provided by the bioanalytical lab or preferred units for presentation of PK parameters) and dose units used in the study.

b. The AUC will be calculated using the linear trapezoidal rule for increasing concentrations and the logarithmic rule for decreasing concentrations (linear up/log down rule).

c. Based on the last observed quantifiable concentration

d. Calculated by dividing the parameter by the dose (mg)

Additional PK parameters may be calculated, as appropriate.

Pharmacokinetic analysis will be carried out where possible using actual blood sampling times postdose. If an actual time is missing, the sample concentration result will be treated as missing unless there is scientific justification to include the result using the nominal time.

 C_{max} , C_{min} , t_{last} and t_{max} will be obtained directly from the concentration-time profiles. If C_{max} occurs at more than 1 timepoint, t_{max} will be assigned to the first occurrence of C_{max} .

The accumulation ratio(s) (AR_{AUC} and AR_{Cmax}) will be calculated as follows:

 $RA_{AUC0-\tau} = AUC_{0-\tau}$ profile day 10 / AUC_{0-\tau} profile day 1

 $RA_{Cmax} = C_{max}$ profile day 10 / C_{max} profile day 1

The parameter AUC_{0-tlast} or other common partial area may be used to determine $RA_{AUC0-\tau}$ if AUC_{0- τ} cannot be reliably calculated for the majority of subjects.

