| Blood sampling e,f                |                               |                | Day 1: predose, 0.25, 0.5, 1, 1.5, 2, 3, 4, 6, 8, 12, 16 and 24 hours postdose
Days 4, 6, 7, 8, and 9: predose
Day 10: predose, 0.25, 0.5, 1, 1.5, 2, 3, 4, 6, 8, 12, 16, 24, 36 and 48 hours
postdose |  |
| Urine sampling e,f                |                               |                | Day 1: predose (spot collection), 0 to 24 hours postdose
Day 10: 0 to 24 hours postdose  |  |

| Study Procedures  | Screening
(Days -28 to -2) | Day -1                                       | Days 1 to 12   | Follow-up
(7 to 10 days
post-final dose) |
|---|-------------------------------|--|--|--|
| Safety and tolerability:  |                               |  |  |  |
| Adverse event recording   | X                             | Х  | Ongoing  | Х  |
| Prior/concomitant medication
monitoring                                    | X                             | Х  | Ongoing  | Х  |
| Clinical chemistry, haematology, coagulation, and urinalysis                  | X                             | Х  | Days 3 and 7: predose
Day 10: 48 hours postdose   | Х  |
| Blood pressure, pulse rate,
respiratory rate, and oral body
temperature | X                             |  | Day 1: predose, 2, 4, and 8 hours postdose
Days 2, 4, and 7: predose
Day 10: predose, 2, 4, 8, 24, and 48 hours postdose         | х  |
| Orthostatic vital signs   | X                             |  | Day 1: predose, 2, 4, and 8 hours postdose
Days 2, 4, and 7: predose
Day 10: predose, 2, 4, 8, 24, and 48 hours postdose         | X  |
| 12-lead ECG   | X                             |  | Day 1: predose and 4 hours postdose
Days 2, 4, and 7: predose and 4 hours postdose
Day 10: predose, 4, 24, and 48 hours postdose | X  |
| C-SSRS  | X                             | Х  | Day 12   | Х  |
| Neurological examination  | X                             | a
10 - 10 - 10 - 10 - 10 - 10 - 10 - 10 - | Days 3, 6, 9, and 12 g  | X  |
| Physical examination  | X h                | X i                               | Prior to discharge on Day 12 i  | X i                                 |

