4.2. Part B

Part B will comprise a multiple-ascending dose, sequential-group design. Overall, it is planned for 24 subjects to be studied in 3 groups (Groups B1 to B3), with each group consisting of 8 subjects. Part B may start following review of the safety and tolerability and PK data for Group A4, at a dose equal or less than given in Groups A1 to A4, provided the predicted exposure is not expected to exceed an exposure already shown to be safe and well tolerated. The dose level cannot be equal to a dose level from Part A if that dose met any of the dose escalation stopping rules.

Potential subjects will be screened to assess their eligibility to enter the study within 28 days prior to the first dose administration. Each subject will participate in 1 treatment period only and reside at the CRU from Day -1 until the morning of Day 12. All subjects will return for a Follow-up visit 7 to 10 days after their final dose.

Based on the ongoing review of available safety, tolerability, and PK data, up to 3 additional non-residential visits may be required. The number of additional visits per subject will not exceed 3 and will not extend beyond 28 days after each final dosing occasion.

In each of Groups B1 to B3, 6 subjects will receive AM1476 and 2 subjects will receive placebo. The dietary state for dosing in Part B will be subject to review of the PK data from the fed/fasted comparison in Part A. For all subjects, dosing is planned to be once daily (QD) on Days 1 to 10, inclusive. However, the dietary state (including fasting requirement and meal compositions), dosing duration, and dosing frequency may be changed following review of safety, tolerability, and PK data from Part A or earlier groups in Part B. The dose regimen will comprise no less than once every 2 days and will not exceed twice daily (BID) dosing. The predicted total daily exposure at the selected dose administered will not exceed an exposure shown to be safe and well-tolerated in Part A. The dosing duration will comprise no fewer than 7 consecutive days and will not exceed 28 consecutive days. There will be a minimum of 6 days between dose escalations for each group.

The total duration of study participation for each subject (from Screening through Follow-up visit) is anticipated to be approximately 7 weeks.

An overview of the study design is shown in Figure 4 and the planned dose levels in Figure 5.

[figure not shown]
[figure not shown]

Figure 4: Study Schematic (Part B)

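### The fallback for the Part B accumulation ratio permits AUC0-tlast, which does not guarantee the same interval on Day 1 and Day 10 and so can overstate accumulation.

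*SAP*

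**What the plan says.** SAP 8.5.1 defines RA_AUC0-tau as AUC0-tau on Day 10 divided by AUC0-tau on Day 1. It then adds a fallback: AUC0-tlast "or other common partial area may be used to determine" the ratio if AUC0-tau "cannot be reliably calculated for the majority of subjects".

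The same section defines AUC0-tlast as the "area under the concentration-time curve from time 0 to the time of the last quantifiable concentration". Its upper limit therefore belongs to the individual profile and is not fixed across days. AUC0-tlast is in the Part A parameter table but not in the Part B table. Under SAP 8.5.1.4, values below the limit of quantification (BLQ) that follow the first measurable concentration are treated as missing.

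The Part B schedule (Protocol Appendix 7) samples "Day 1: predose, 0.25, 0.5, 1, 1.5, 2, 3, 4, 6, 8, 12, 16 and 24 hours postdose", and on the last dosing day "Day 10: predose, 0.25, 0.5, 1, 1.5, 2, 3, 4, 6, 8, 12, 16, 24, 36 and 48 hours" after the dose. In the planned regimen, "dosing is planned to be once daily (QD) on Days 1 to 10, inclusive", so tau is 24 h.

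No section cuts the Day 10 profile at tau or requires equal end times for this ratio. SAP 8.5.1.3 does impose that condition on renal clearance, where urinary amount and AUC must run to the same end time.

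**The concern.** A ratio of two areas measures accumulation only if both cover the same interval after the dose. The fallback names an area whose interval can differ between numerator and denominator. In linear, accumulating kinetics, Day 10 concentrations are at least as high as Day 1 concentrations at the same time after dose. Day 10 tlast is therefore the same or later, and a mismatch from this cause pushes the ratio up. With 6 active subjects per group, averaging does not remove an error that acts in one direction.

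RA_AUC0-tau is a listed Part B secondary endpoint. Protocol 1.9 says the PK data will help establish doses and regimen for patient studies. A mismatched ratio would be reported under the same name as the true one, and a reader could not tell from the summary that part of it comes from a longer interval.

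**Working it through.** **No figure to reproduce.** The documents give no accumulation ratio, human half-life, absorption rate or LLOQ. The kinetic inputs below are assumptions, shown over a range.

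**Schedule check.** Part B has 13 samples on Day 1, 5 troughs, 15 samples on Day 10 and 3 extra: 13 + 5 + 15 + 3 = 36, and 36 × 3.0 mL = 108.0 mL. Both totals match Protocol Appendix 3, so the 24 h and 48 h sampling limits are as read.

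**Model.** One compartment, oral, once daily, scaled so that dose × F/V = 1. With k = ln 2 / half-life, the concentration at time t after dose n is

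C(t) = Σ (j = 0 to n−1) ka/(ka − k) × [exp(−k(t + 24j)) − exp(−ka(t + 24j))].

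This was evaluated at the protocol times. Areas use the SAP's "linear trapezoidal rule for increasing concentrations and the logarithmic rule for decreasing concentrations". BLQ values count as zero before the first measurable value and as missing after it. The true ratio is AUC0-24 Day 10 / AUC0-24 Day 1 with every sample quantifiable.

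**When the fallback applies.** The main route is a BLQ 24 h sample on Day 1. The LLOQ must then exceed the Day 1 24 h level, which for ka of 1 to 2 /h is 8–10% of Day 1 Cmax at half-life 6 h, 29–32% at 12 h and 54–57% at 24 h.

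**Two worked cases (ka 2/h; LLOQ as % of Day 1 Cmax).**

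| | Half-life 6 h, LLOQ 20% | Half-life 12 h, LLOQ 30% |
|---|---|---|
| Sample that decides | 16 h: 19.9% on Day 1, 21.2% on Day 10 | 24 h: 28.7% on Day 1, 38.2% on Day 10 |
| tlast, Day 1 / Day 10 | 12 h / 16 h | 16 h / 24 h |
| Fallback ratio | 7.692/6.335 = 1.21 | 17.288/10.213 = 1.69 |
| True ratio | 8.632/8.057 = 1.07 | 17.288/12.831 = 1.35 |
| Inflation | 13% | 26% |
| Same end time on both days | AUC0-12: 6.785/6.335 = 1.07 | AUC0-16: 13.797/10.213 = 1.35 |

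**Grid.** Half-lives 2, 3, 4, 6, 8, 12, 16 and 24 h; LLOQ 1, 2, 5, 10, 15, 20, 25, 30, 40 and 50% of Day 1 Cmax.

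- With ka 1/h, the Day 1 24 h sample is BLQ in 43 combinations. tlast differs between days in 6 of them, with inflation of 13, 15, 28, 31, 35 and 40%. The 40% case needs an LLOQ at half of Cmax (half-life 8 h).
- With ka 2/h, the sample is BLQ in 45 combinations. tlast differs in 5, with inflation of 13, 23, 26, 31 and 32%.
- In all the others tlast is equal. The ratio is then within about 1% of the truth for LLOQ up to 40% of Cmax, and within 4% at 50%, where an early Day 1 sample can also fall below the limit.

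**Finer scan (ka 1/h, every LLOQ that gives Day 1 tlast = 16 h).** The largest inflation is 0% at half-life 2 h, 3% at 3 h, 6% at 4 h, 13% at 6 h, 19% at 8 h, 28% at 12 h and 35% at 16 h. Up to 16 h, the mismatch is never more than 16 h against 24 h. It comes from tlast moving within the first 24 h, not from the 36 h and 48 h samples.

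**Effect of a common end time.** Restricting both days to the shared interval in the 11 mismatched cases brings the ratio to within about 1% of the truth for LLOQ up to 40% of Cmax, and within about 3% at 50%.

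**The case against.** The strongest defence is that the rule is optional, conditional and already contains the remedy. It says may, it also offers a common partial area, and it applies only when AUC0-tau fails for most subjects. The plan works to keep AUC0-tau available: SAP 8.5.1.2 calculates it when the tau sample is within 60 minutes of nominal, and SAP 8.5.1.4 allows a missing Day 10 end-of-interval value to be replaced by the predose value. The ratio is one of 13 listed Part B PK endpoints, is only summarised, and enters no test or model. RA_Cmax is unaffected. All concentrations are listed, so the ratio could be recomputed.

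Most of this stands, and it limits the size of the point. It does not remove it. The word common shows the intent, but AUC0-tlast is named as an acceptable choice and does not deliver a common interval. The trigger is also set by the majority, so the minority with quantifiable late samples could still get mismatched intervals.

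Two stronger readings are tempting, and the documents do not support them.

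- **That the fallback compares 48 h with 24 h.** With e = 2^(−24/half-life), and neglecting the absorption phase, that contrast would give (1 + e)/(1 − e) instead of 1/(1 − e): 1.13 for 1.07 at 6 h, 1.67 for 1.33 at 12 h, 3.0 for 2.0 at 24 h. It needs a quantifiable 24 h sample on Day 1, and then AUC0-tau is normally calculable and the fallback is not used. These figures are not the expected size.
- **That Day 10 tlast is always later.** Sampling is discrete (8, 12, 16, 24 h), so modest accumulation often leaves tlast where it was.

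**Conclusion.** The point holds as a gap in the rule: the fallback can overstate accumulation, but need not. SAP 8.5.1 permits an area without a guaranteed common interval, and where accumulation moves tlast the error is upward.

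With a BLQ 24 h sample on Day 1, bias is essentially nil in most of the assumed scenarios. Where tlast differs it is mostly about 13–35%. It is smaller at half-lives of 3 to 4 h, and it reached 40% in one case with an LLOQ at half of Cmax. These sizes rest on assumed linear one-compartment kinetics, ka of 1 to 2 /h, half-lives up to 16 h and LLOQ up to 50% of Cmax. The direction needs only linear kinetics with accumulation.

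The importance is minor to moderate: a descriptive secondary PK endpoint, exposed only if the fallback is used.

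**What to change.** In SAP 8.5.1, remove the unqualified AUC0-tlast from the fallback sentence and replace the sentence with wording such as:

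*If AUC0-tau is not reliable for more than half of the subjects, the accumulation ratio will be AUC0-t on Day 10 divided by AUC0-t on Day 1. The same t applies to both days within a subject: the latest scheduled time, no later than tau, with a quantifiable concentration on both days. The result will be labelled a partial-area accumulation ratio and t will be listed for each subject.*

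The limit at tau also covers a change of dosing frequency, which the protocol allows. The label stops the substitute from being read as RA_AUC0-tau. The cost is one SAP sentence and one table footnote. It needs no new samples or assessments and no change to the protocol.

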8.5.1.1. Criteria for the Calculation of Apparent Terminal Elimination Rate Constant and Half-Life

The start of the terminal elimination phase for each subject will be defined by visual inspection and generally will be the first point at which there is no systematic deviation from the log-linear decline in concentrations.

The apparent terminal elimination rate constant (λ_z) will only be calculated when a reliable estimate can be obtained using at least 3 data points, preferably not including C_{max} , and the adjusted coefficient for determination of exponential fit (R²-adj) of the regression line is ≥ 0.7 . Parameters requiring λ_z in their calculation (eg, AUC_{0-∞}, t_{1/2}, CL/F [profile day 1 only] and V_z/F) will only be calculated if the R²-adj value of the regression line is ≥ 0.7 .

The following regression-related diagnostic PK parameters will be determined where possible:

Parameter	Units ^a	Definition
λ_z	1/h	apparent terminal elimination rate constant
λ_z Upper	h	end of exponential fit
λ_z Lower	h	start of exponential fit
$\lambda_z N$		number of data points included in the log-linear regression
λ_z Span Ratio		time period over which λ_z was determined as a ratio of $t_{1/2}$
R ² -adj		adjusted coefficient for determination of exponential fit

Where possible, the span of time used in the determination of λ_z (ie the difference between λ_z Upper and λ_z Lower) should be ≥ 2 half-lives. If the λ_z Span Ratio is <2, the robustness of the $t_{1/2}$ values will be discussed in the CSR.

8.5.1.2. Criteria for Calculation and Reporting of Area Under the Concentration-time Curve

The minimum requirement for the calculation of area under the concentration-time curve (AUC) will be the inclusion of at least 3 consecutive concentrations above the lower limit of quantification (LLOQ). If there are only 3 consecutive concentrations, at least 1 should follow C_{max} .

If the extrapolated area is >20%, AUC_{0- ∞} (and derived parameters) may be excluded from summary statistics and statistical analysis at the discretion of the sponsor or pharmacokineticist.

If $AUC_{0-\infty}$ cannot be determined reliably for all subjects and/or dose levels, an alternative AUC measure, such as AUC to a fixed timepoint or $AUC_{0-tlast}$, may be used in the statistical analysis of dose proportionality/food-effect.

If the end of the dosing interval PK blood sample is collected slightly early (ie, the 24 hour sample), the actual sampling time of the scheduled τ sample (24 hours) may be used for the

calculation of AUC_{0- τ}. However, the AUC_{0- τ} parameter will be calculated if the τ sample is within 60 minutes of the nominal sampling time.

8.5.1.3. Calculation of Urinary Parameters

The amount of drug excreted in urine (Ae) in urine for AM1476 and urine collection interval (t_1-t_2) will be calculated as the product of urine AM1476 concentration and urine volume. Where only urine sample weight is supplied, a specific gravity of 1 g/mL will be assumed, and it will be considered equivalent to urine volume. A total cumulative Ae_{0-x h} will be calculated by summing the Ae_{t1-t2} values over the 0-x h interval, where x = the end of the last collection time interval.

The percentage of the dose administered over the time interval t1 to t2 (fe_{t1-t2}) as AM1476 will be calculated for each urine collection interval as follows:

 $fe_{t1-t2} = (Ae_{t1-t2} / dose) \times 100.$

Cumulative $fe_{0-x h}$ will be calculated by summing the fe_{t1-t2} values over the 0-x h period in the same manner as $Ae_{0-x h}$.

Renal clearance (CL_R) will be calculated over 0-t2 according to the following formula, where cumulative Ae and AUC are calculable to the same end time (t2):

 $CL_R = Ae_{0-t2} / AUC_{0-t2}$.

Alternatively, $AUC_{0-\infty}$ may be used (applicable to profile day 1 only) if urinary excretion of the dose is considered to be complete and $AUC_{0-\infty}$ is well characterised.

8.5.1.4. Criteria for Handling Concentration Below the Limit of Quantification or Missing Concentrations for Pharmacokinetic Analysis

Plasma concentrations below the limit of quantification (BLQ) will be assigned a value of 0 before the first measurable concentration and thereafter BLQs will be treated as missing. The following rules apply with special situations defined below:

- If an entire concentration-time profile is BLQ, it will be excluded from PK analysis.
- Where 2 or more consecutive concentrations are BLQ at the end of a profile, the profile will be deemed to have terminated and any further quantifiable concentrations will be set to missing for the calculation of the PK parameters, unless they are considered to be a true characteristic of the profile of the drug.
- If a predose plasma concentration is missing, it may be set to 0 by default.
- For multiple dose occasion parts of the study only (profile day 10), if the concentration at τ (C_{τ}) is missing, this may be substituted with the predose concentration. Similarly, if the predose concentration is missing, this may be substituted with C_{τ}.

Urine concentrations that are BLQ will be set to 0 for the calculation of $Ae_{t1-t2.}$

8.5.1.5. Treatment of Outliers in Pharmacokinetic Analysis

If a value is considered to be anomalous due to being inconsistent with the expected PK profile, it may be appropriate to exclude this point from the PK analysis. However, the exclusion of data must have strong justification and will be documented in CSR.

Any quantifiable predose concentration value on the first dosing day of all parts of the study (profile day 1) will be considered anomalous and set to missing for the PK analysis. This will be set to 0 by default in Phoenix WinNonlin.

